1. INTRODUCTION

The statistical analysis plan (SAP) for the 7376763989PAHPB2006 phase 2 trial describes the statistical analyses and definitions to assess the efficacy, and safety of the study intervention including JNJ-73763989, JNJ-56136379, Nucleos(t)ide analogs (NA), and pegylated interferon alpha-2a (PegIFN- α 2a) in virologically suppressed participants with chronic hepatitis B (CHB) virus infection. In the rest of the document the abbreviations JNJ-3989 and JNJ-6379 are used to refer to the treatments JNJ-73763989 and JNJ-56136379, respectively. Prior to Protocol Amendment 3, the study intervention also included JNJ-6379. Note that as of Protocol Amendment 3, JNJ-6379 has been removed as study intervention and the study will continue with JNJ-3989, NA and PegIFN- α 2a only. Participants had to stop JNJ-6379 treatment immediately after the implementation of Urgent Safety Measure (USM) and approval of the protocol amendment 3.

This study is part of the platform trial PLATFORMPAHPB2001 in participants with CHB. The protocol for 73763989PAHPB2006 constitutes the Intervention Specific Appendix that describes all the specific and/or additional features of this study complementing the common design elements of the platform trial described in the Master Protocol.

This SAP is to be interpreted in conjunction with the clinical protocol Amendment-3 finalized on 04 October 2021, and with the Master Protocol Amendment-3 for PLATFORMPAHPB2001 finalized on 21 January 2021.

Details of the pharmacokinetic (PK) and pharmacokinetic/pharmacodynamics (PK/PD) analyses will be described in a separate analysis and modeling plan.

1.1. Objectives and Endpoints

Objectives	Endpoints
Primary	

 To evaluate the efficacy in terms of HBsAg levels of the study intervention (i.e. JNJ-3989 + JNJ-6379^d + NA and PegIFN-α2a). 	
 Proportion of participants with a reduction of at least 2 log₁₀ IU/mL in HBsAg levels from baseline to Week 24 (end of study intervention [EOSI]).
Secondary	

 To evaluate the safety and tolerability of the study intervention. 	
 Safety and tolerability including but not limited to the proportion of participants with (serious) adverse events (S)AEs and abnormalities in clinical laboratory tests (including hematology, blood biochemistry, blood coagulation, urinalysis, urine chemistry, and renal biomarkers), 12-lead electrocardiograms (ECGs), vital signs, and ophthalmic and physical examinations throughout the study.

 To evaluate the efficacy of the study intervention at the end of the 24-week treatment period. 	
 Proportion of participants meeting the protocol-defined NA treatment completion criteria at EOSI.

 To evaluate the efficacy of the study intervention as measured by blood markers (such as HBsAg, HBeAg^a, HBV DNA, and alanine aminotransferase [ALT]) during the study intervention and follow-up (FU) period. 	
 Proportion of participants with HBeAg^a, HBsAg, HBV DNA, and ALT levels below/above different cut-offs. Proportion of participants with HBsAg and/or HBeAg^a seroconversion.

Objectives	Endpoints
	
 Change from baseline over time in HBsAg, HBeAg^a, and/or HBV DNA. Time to achieve HBsAg and/or HBeAg^a seroclearance/seroconversion, and/or HBV DNA < lower limit of quantification (LLOQ).

 To evaluate the frequency of virologic breakthrough^b during the 24-week treatment period, as well as during the FU period for participants who continue treatment with NA. 	
 Proportion of participants with virologic breakthrough^b.

 To evaluate the efficacy of the study intervention during the FU period. 	
 Proportion of participants with HBsAg seroclearance at Week 48 (ie, 24 weeks after completion of all study interventions at Week 24) without re-starting NA treatment. Proportion of participants with HBV DNA <LLOQ at Week 48 (ie, 24 weeks after completion of all study interventions at Week 24) without re-starting NA treatment. Frequency of virologic and/or biochemical flares. Proportion of participants requiring NA re-treatment.

 To evaluate the pharmacokinetics (PK) of JNJ-3989 (JNJ-3924 and JNJ-3976), and optionally of JNJ-6379, NA and PegIFN-α2a. 	
 PK parameters of JNJ-3989 (JNJ-3924 and JNJ-3976). Optionally, PK parameters of JNJ-6379, NA and/or PegIFN-α2a compared to historical data.
Exploratory	

 To explore host and viral baseline and on-treatment markers associated with end of treatment and/or off-treatment response. 	
 Association of baseline characteristics and baseline/on-treatment host and viral blood markers (such as age and HBsAg levels) with selected on or off-treatment efficacy variables.

 To explore changes in the severity of liver disease. 	
 Changes in fibrosis (accounting to Fibroscan liver stiffness measurements) at EOSI and the end of the FU period versus baseline.

 To explore efficacy of the study intervention in terms of changes in HBV RNA and hepatitis B core-related antigen (HBcrAg) levels during the study intervention and FU period. 	
 Changes from baseline in HBV RNA and HBcrAg levels over time.

 To explore the relationship of PK with selected pharmacodynamic (PD) parameters of efficacy and safety. 	
 Relationship of various PK parameters with selected efficacy and safety endpoints.

 To explore the effect of PegIFN-α2a coadministration on the PK of JNJ-3989 (JNJ-3924 and JNJ-3976) and JNJ-6379^c, as applicable (PK substudy). 	
 Effect of PegIFN-α2a coadministration on the PK of JNJ-3989 (JNJ-3924 and JNJ-3976) and JNJ-6379, as applicable.

 To explore the HBV genome sequence during the study intervention and FU period. 	
 Assessment of intervention-associated mutations over time.

 To explore HBV-specific T-cell responses during the study intervention and FU period.^c 	
 Changes from baseline in HBV-specific peripheral blood T-cell responses over time.^c

Objectives	Endpoints

 To explore the efficacy of NA re-treatment in participants who meet the criteria for NA re-treatment. 	
 Proportion of participants who reach HBV DNA <LLOQ after re-start of NA treatment during the FU period.

- a. In HBeAg-positive participants only.
- b. Confirmed on-treatment HBV DNA increase by $>1 \log_{10}$ IU/mL from nadir or confirmed on-treatment HBV DNA level >200 IU/mL in participants who had HBV DNA level <LLOQ of the HBV DNA assay.
- c. Peripheral blood mononuclear cell (PBMC) samples for immune analyses will be collected at selected sites only.
- d. As per Protocol Amendment 3, JNJ-6379 has been removed as study intervention and the study will continue with JNJ-3989, NA and PegIFN- α 2a only. Participants had to stop JNJ-6379 treatment immediately.
- e. Not all participants completed treatment with JNJ-6379, as JNJ-6379 has been removed as study intervention with the implementation of Protocol Amendment 3.

1.2. Study Design

This is a Phase 2a, open-label, single-arm, multicenter study to assess efficacy, safety, tolerability and pharmacokinetics of treatment with JNJ-3989, JNJ-6379 (as applicable), NA, and PegIFN- α 2a in virologically suppressed patients with chronic hepatitis B virus infection. Prior to Protocol Amendment 3, the study intervention also included JNJ-6379. Note that as of Protocol Amendment 3, JNJ-6379 has been removed as study intervention and the study will continue with JNJ-3989, NA and PegIFN- α 2a only. Participants had to stop JNJ-6379 treatment immediately after the implementation of Urgent Safety Measure (USM) and approval of the protocol amendment 3.

Approximately 50 virologically suppressed CHB-infected participants, 18-65 years (inclusive) of age, will be enrolled in this study. Approximately 40% HBeAg-positive participants will be enrolled.

[figure not shown]
The study will be conducted in 4 periods:

- Screening period (4 weeks [if necessary, can be extended to a maximum of 8 weeks decided on a case-by-case basis and in agreement with the sponsor]).
- Treatment Period 1 (12 weeks) consisting of combination treatment with JNJ-3989 + NA.
- Treatment Period 2 (12 weeks) adding PegIFN- α 2a to the combination treatment regimen of Treatment Period 1.
- Follow-up (FU) Period (48 weeks).

The total duration of individual participation will be up to 76 weeks (including 4 weeks of screening).

A schematic of the trial prior to Protocol Amendment 3 is presented in [Figure 1](#).

Figure 1: Schematic Overview of the Study – Prior to Protocol Amendment 3

[figure not shown]

ALT: alanine aminotransferase; DNA: deoxyribonucleic acid; EOS: end of study; EOSI: end of study intervention; FU: follow-up; HBeAg: hepatitis B e antigen; HBsAg: hepatitis B surface antigen; HBV: hepatitis B virus; JNJ-3989: JNJ-73763989; JNJ-6379: JNJ-56136379; LLOQ: lower limit of quantification; n: number of participants; NA: nucleos(t)ide analog; PegIFN-α2a: pegylated interferon alpha-2a; ULN: upper limit of normal; Q4W: every 4 weeks; QD: once daily; QW: once weekly.

^a. If NA treatment completion criteria (HBsAg <10 IU/mL, and HBeAg-negative, and HBV DNA <LLOQ, and ALT <3x ULN) have been met at Week 24, NA will be stopped at the next scheduled visit (ie, FU Week 2), otherwise NA treatment will continue during the complete FU period.

A schematic of the trial as of Protocol Amendment 3 is presented in [Figure 2](#).

Figure 2: Schematic Overview of the Study – As of Protocol Amendment 3

ALT: alanine aminotransferase ; DNA: deoxyribonucleic acid; EOS: end of study; EOSI: end of study intervention; FU: follow-up; HBeAg: hepatitis B e antigen; HBsAg: hepatitis B surface antigen; HBV: hepatitis B virus; JNJ-3989: JNJ-73763989; LLOQ: lower limit of quantification; n: number of participants; NA: nucleos(t)ide analog;

PegIFN- α 2a: pegylated interferon alpha-2a; ULN: upper limit of normal; Q4W: every 4 weeks; QD: once daily; QW: once weekly.

^a If NA treatment completion criteria (HBsAg <10 IU/mL, and HBeAg-negative, and HBV DNA <LLOQ, and ALT <3x ULN) have been met at Week 24, NA will be stopped at the next scheduled visit (ie, FU Week 2), otherwise NA treatment will continue during the complete FU period.

Prior to Protocol Amendment 3:

Enrolled participants (approximately n=50) will start Treatment Period 1 with triple combination treatment (JNJ-3989 [200 mg once every 4 weeks (Q4W)] + JNJ-6379 [250 mg once daily (QD)] + NA [tenofovir disoproxil (TeD; 245 mg), or tenofovir alafenamide (TAF; 25 mg), or entecavir (ETV; 0.5 mg) (QD)]) for a duration of 12 weeks.

At Week 12, participants who still meet the eligibility criteria for PegIFN- α 2a will start Treatment Period 2 with quadruple combination treatment (JNJ-3989 [200 mg once every 4 weeks (Q4W)] + JNJ-6379 [250 mg once daily (QD)] + NA [tenofovir disoproxil (TeD; 245 mg), or tenofovir alafenamide (TAF; 25 mg), or entecavir (ETV; 0.5 mg) (QD)] + PegIFN- α 2a [180 μ g once weekly]) for a duration of 12 weeks.

Participants no longer meeting the PegIFN- α 2a eligibility criteria at Week 12 will continue with the Period 1 treatment until Week 24.

At Week 24, all participants will stop treatment with JNJ-3989 + JNJ-6379 + PegIFN- α 2a and start the FU Period. NA treatment will be continued during the FU phase in patients not meeting the NA completion criteria.

Participants will be considered to have completed the study if they have completed all the assessments of the end of study (EOS) visit (ie, FU Week 48).

An internal data review committee (DRC) will be commissioned for monitoring safety of participants enrolled in this study. In addition, an Independent Flare Expert Panel (IFLEP) will be appointed.

As of Protocol Amendment 3:

Enrolled participants will start Treatment Period 1 with the following combination treatment regimen (JNJ-3989 [200 mg once every 4 weeks (Q4W)] + NA [tenofovir disoproxil (TeD; 245 mg), or tenofovir alafenamide (TAF; 25 mg), or entecavir (ETV; 0.5 mg) (QD)]) for a duration of 12 weeks.

At Week 12, participants who still meet the eligibility criteria for PegIFN- α 2a will start Treatment Period 2 with triple combination treatment (JNJ-3989 [200 mg once every 4 weeks (Q4W)] + NA [tenofovir disoproxil (TeD; 245 mg), or tenofovir alafenamide (TAF; 25 mg), or entecavir (ETV; 0.5 mg) (QD)] + PegIFN- α 2a [180 μ g once weekly]) for a duration of 12 weeks.

Participants no longer meeting the PegIFN α 2a eligibility criteria at Week 12 will continue with the Period 1 treatment until Week 24.

At Week 24, all participants will stop treatment with JNJ-3989 + PegIFN- α 2a and start the FU Period. NA treatment will be continued during the FU phase in patients not meeting the NA completion criteria.

Participants will be considered to have completed the study if they have completed all the assessments of the end of study (EOS) visit (ie, FU Week 48).

An internal data review committee (DRC) will be commissioned for monitoring safety of participants enrolled in this study. In addition, an Independent Flare Expert Panel (IFLEP) will be appointed.

2. STATISTICAL HYPOTHESES

As this is an exploratory proof of concept (PoC), single-arm study, no formal hypothesis has been formulated.

3. SAMPLE SIZE DETERMINATION

No formal sample size calculation was performed, as this is a single-arm study for exploratory and PoC purposes. However, with a sample size of 50 participants having data for the primary efficacy endpoint at Week 24, if at least 25 (50%) participants are responders, it can be concluded with 90% confidence that the true response rate is at least 0.38, with a confidence interval (CI) width of 0.248 (90% CI: 0.376-0.624). With a sample size of 20 participants (for one of the interim analyses [IAs]) the precision of the estimate of the primary efficacy endpoint decreases, as the two-sided 90% CI width increases. For the same assumed proportion of responders of 50% (10 out of 20 participants), the 90% CI width becomes 0.396. [Table 1](#) shows the 90% CI and the corresponding width for proportion of responders of 0.30, 0.50, 0.70, and 0.90.

Table 1: Confidence intervals for a range of proportions

Proportion of responders	N=20		N=50	
	90% CI*	Width of CI	90% CI*	Width of CI
0.30	0.140-0.508	0.368	0.195-0.424	0.229
0.50	0.302-0.698	0.396	0.376-0.624	0.248
0.70	0.492-0.860	0.368	0.576-0.805	0.229
0.90	0.717-0.982	0.265	0.801-0.960	0.159

CI: confidence interval.

* Clopper-Pearson exact method is used.

4. POPULATIONS (ANALYSIS SETS) FOR ANALYSIS

Due to a potential impact of future Coronavirus Disease (COVID-19) pandemics on the study data collection, study treatment adherence and study conduct, the modified Full Analysis Set (mFAS) and modified IFN-FAS (mIFN-FAS) are defined to target the estimation of effects without the pandemic-related influences.

The primary set for the efficacy analyses will be the FAS set, and for the safety analyses the safety set. The IFN-FAS and modified FAS/IFN-FAS analysis sets will be used if there is a difference of at least 2 participants between analysis sets.

Table 2: Analysis Sets for Analysis

Analysis Sets	Description
Screened	All participants who signed the ICF for the Master Protocol and an ICF specific for the ISA.
Enrolled	All participants who were enrolled in this ISA.
Full Analysis Set (FAS)	All participants who were enrolled and who received at least 1 dose of study intervention within this ISA.
Modified FAS	All participants who were enrolled and who received at least 1 dose of study intervention excluding those participants who, because of COVID-19 or similar pandemics related reasons, withdrew prematurely from the study prior to Week 24 (end of study intervention [EOSI]), or had no efficacy assessment for the primary endpoint. COVID-19 or similar pandemics related reasons may include for example missed visits due to travel restriction, shortage of lab kits at the planned visit, missed collection of blood sample at key time points for the primary efficacy endpoint, etc.
IFN-FAS	All participants who were enrolled and who received at least 1 dose of PegIFN- α 2a within this ISA.
Modified IFN-FAS	All participants who were enrolled and who received at least 1 dose of PegIFN- α 2a excluding those participants who, because of COVID-19 or similar pandemics related reasons, withdrew prematurely from the study prior to Week 24 (EOSI), or had no efficacy assessment for the primary endpoint. COVID-19 or similar pandemics related reasons may include for example missed visits due to travel restriction, shortage of lab kits at the planned visit, missed collection of blood sample at key time points for the primary efficacy endpoint, etc.
Safety	All participants who received at least 1 dose of study intervention. Participants will be analyzed according to the study intervention they actually received.
Pharmacokinetics Analysis Set	All participants who received at least 1 dose of study intervention and have at least 1 valid blood sample drawn for PK analysis.

5. STATISTICAL ANALYSES

5.1. General Considerations

The SAP will use throughout the document the following definitions:

- *Study treatment* refers to: JNJ-3989, JNJ-6379, NA, and PegIFN- α 2a
- *Study agent* refers to: JNJ-3989, JNJ-6379, and PegIFN- α 2a
- *Study intervention* refers to:
 - Treatment Period 1:
 - JNJ-3989 + JNJ-6379 + NA
 - JNJ-3989 + NA
 - Treatment Period 2:

- JNJ-3989 + JNJ-6379 + NA + PegIFN- α 2a
- JNJ-3989 + NA + PegIFN- α 2a

NA can be either ETV, TeD or TAF.

5.1.1. Analysis Phase

The analysis phases are defined in [Table 3](#) below.

Table 3: Analysis Phases Start and End Dates

Analysis Phase	Start date	End date
Screening	The date of signing the informed consent	1 day before the first study agent intake (excluding PegIFN- α 2a)
Treatment Period 1	Date of first study agent intake (excluding PegIFN- α 2a)	For participants who receive PegIFN-α2a: Min [Date of first PegIFN- α 2a intake - 1 day, cut-off date ^b]
		For participants who do not receive PegIFN-α2a: Date of Week 12 study agent intake - 1 day
		For participants who discontinue treatment before Week 12: Max [last intake date of any study agent, study agent discontinuation date, early study withdrawal visit date] + 5 days ^a or cut-off date ^b , whichever occurs first
Treatment Period 2	For participants who receive PegIFN-α2a: Date of first PegIFN- α 2a intake	For participants who did not withdraw from the study prior to the projected/actual Week 24 visit date: Max [last intake date of any study agent, study agent discontinuation date, projected/actual Week 24 visit date] + 5 days ^a or cut-off date ^b , whichever occurs first
	For participants who do not receive PegIFN-α2a: Date of Week 12 study agent intake	
	Otherwise: missing	
Follow-up	Participants who did not withdraw informed consent during treatment period 1 or 2: Max [End date of Treatment Period 1, End date of the Treatment Period 2] + 1 day	Max [study discontinuation date, study completion date] or cut-off date ^b , whichever occurs first
	Otherwise: missing	Otherwise: missing

^a Addition of 5 days is only applicable for Adverse Events and Concomitant Medications.

^b Cutoff dates will be defined to match the prespecified timepoints for DRC safety monitoring, interim analyses, the primary and final analyses, respectively.

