AFP: alpha-fetoprotein; ALP: alkaline phosphatase; ALT: alanine aminotransferase; AST: aspartate aminotransferase; CKD-EPI: Chronic Kidney Disease Epidemiology Collaboration; CRF: case report form; CT: computed tomography; D/d: day; DAIDS: Division of Acquired Immunodeficiency Syndrome; DBP: diastolic blood pressure; DNA: deoxyribonucleic acid; ECG: electrocardiogram; eGFR: estimated glomerular filtration rate; EOS: end of study; EOSI: end of study intervention; FSH: follicle-stimulating hormone; FU: follow-up; GI = giga; HBe: hepatitis B core protein; HBe(Ag): hepatitis B e (antigen); HBcrAg: hepatitis B core-related antigen; HBs(Ag): hepatitis B surface (antigen); HBV: hepatitis B virus; HCC: hepatocellular carcinoma; HIV-1 (-2): human immunodeficiency virus type 1 (type 2); HLA: human leukocyte antigen; ICF: informed consent form; IgM: immunoglobulin M; INR: International Normalized Ratio; ISA: intervention-specific appendix; MRI: magnetic resonance imaging; NA: nucleos(t)ide analog; PBMC: peripheral blood mononuclear cells; PegIFN- α 2a: pegylated interferon alpha-2a; PK: pharmacokinetic; RBC: red blood cell; RNA: ribonucleic acid; SBP: systolic blood pressure; T4: thyroxine; TSH: thyroid stimulating hormone; ULN: upper limit of normal; W: week; WD: withdrawal.

- a. All study visits are to be scheduled relative to the baseline (Day 1) visit date. All follow-up study visits are to be scheduled relative to the Week 24/EOSI visit. An unscheduled visit can be performed upon the investigator's discretion, in case of HBV DNA elevations, ALT elevations, other signs of worsening of liver disease, or for any other reason.
- b. If necessary (eg, for operational reasons), the Screening Period may be extended up to a maximum of 8 weeks in agreement with the sponsor.
- c. Day 1 samples are to be collected before the first dose of study intervention.
- d. All assessments (with the exception of the sparse and intensive PK samples) should be performed before administration/intake of JNJ-3989 and NA. If applicable, weekly PegIFN- α 2a administration should preferably be done on the same day of the week in the evening by self-injection. If desired, participants can also choose to have the administration of PegIFN- α 2a performed on site irrespective of the time of day. For participants in Japan, weekly administration of PegIFN- α 2a must be performed at the study site by the investigator or his/her designee.

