5.1.2.2. Treatment Period 2 Relative Day

The treatment period 2 start date (TP2 Day 1) is defined as the date of first PegIFN- α 2a injection for those who receive PegIFN- α 2a in treatment period 2, and the date of Week 12 agent intake for those who don't receive PegIFN- α 2a. Efficacy and safety assessments during the TP2 will be assigned an analysis study day relative to this date, unless otherwise specified.

The study day in the TP2 phase (TP2 ADY) is defined as:

$$TP2\ ADY = \text{visit date} - TP2\ \text{start date} + 1$$

for visits on or after TP2 Day 1.

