5.1.3. Visit Windows

As participants do not always adhere to the protocol visit schedule, the following rules are applied to assign actual visits to analysis visits. All visits for all assessments (safety, efficacy or PK) will

be uniquely allocated within each phase to an analysis time point based on the analysis relative day (ADY) compared with the target day based on Table 4. All assignments will be made in chronological order. Once a visit date is assigned to a visit window, it will no longer be used for a later time point except for the end of treatment period 1 (EOT1), end of treatment period 2 (EOT2), and end of study (EOS) visits. If a participant has 2 or more actual visits in one visit window, the visit closest to the target day will be used as the protocol visit for that visit window. The other additional visit(s) will not be used in the summaries or analyses, but they can be used for determination of clinically important endpoints. If 2 actual visits are equidistant from the target day within a visit window, the later visit is used. If there are two or more measurements on the same day, then the last measurement in chronological order will be used. If the time of the assessment is not available, the highest record/sequence number will be selected.

The listings will include all measurements, also those multiple assessments with the same visit window/phase. Spaghetti plots will also display all measurements.

End of treatment period 1 (i.e. EOT1), end of treatment period 2 (i.e. EOT2) and end of study (i.e. EOS) time points will be included in all analyses over time unless stated otherwise.

Table 4 provides the analysis time points and time intervals for each visit per analysis phase.

Table 4: Visit Windows

a) Screening, Treatment Period 1, and Treatment Period 2

Analysis phase	Target day	Analysis time point (Week)	Analysis time point (label)	Time interval (days)
Screening	$-\infty$	-1	Screening	<0
Treatment period 1	1	0	Baseline	Pre-dose: 1
	15	2	Week 2	[2,22]
	29	4	Week 4	[23,43]
	57	8	Week 8	[44,81]
	85 ^a	12.1	Week 12 period 1	[82, 92] ^a
	Last visit in treatment period 1	12.15 ^b	EOT1 ^b	
Treatment period 2	85 ^a	12.2	Week 12 period 2	[82, 92] ^a
	99	14	Week 14	[93,106]
	113	16	Week 16	[107,127]
	141	20	Week 20	[128,155]
	169	24	Week 24	[156,183]
	Last visit in treatment period 2	25 ^c	EOT2 ^c	

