^a Day 85 is the target day for the first administration of PegIFN- α 2a. Time interval [82-92] was selected to align the visit window with the protocol Schedule of Activities for Week 12. Any assessments performed before the administration of PegIFN- α 2a (date/time) at week 12 will be considered under treatment period 1 (Week 12 period 1) and assessments after the administration of PegIFN- α 2a (date/time) will be considered as treatment period 2 (Week 12 period 2).

^b End of treatment period 1 (EOT1) visit will be the last visit of treatment period 1.

^c End of treatment period 2 (EOT2) visit will be the last visit of treatment period 2.

b) Follow-up

Analysis phase	FU Target day	Analysis time point (Week)	Analysis time point (label)	Time interval (FU days)
Follow-up	15	26	Follow-up Week 2	[1, 22]
	29	28	Follow-up Week 4	[23, 43]
	57	32	Follow-up Week 8	[44, 71]
	85	36	Follow-up Week 12	[72, 99]
	113	40	Follow-up Week 16	[100, 127]
	141	44	Follow-up Week 20	[128, 155]
	169	48	Follow-up Week 24	[156, 183]
	197	52	Follow-up Week 28	[184,211]
	225	56	Follow-up Week 32	[212, 239]
	253	60	Follow-up Week 36	[240, 267]
	281	64	Follow-up Week 40	[268, 295]
	309	68	Follow-up Week 44	[296,323]
	337	72	Follow-up Week 48	[324, +∞]
	last visit in the study	999 ^a	EOS ^a	

^a End of study (EOS) visit (last available data during the follow-up phase) will be the last visit in the study.

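### SAP Table 3 and Table 4 footnote a put the same-day pre-dose Week 12 assessment in different treatment periods, no rule says which prevails, and participants without PegIFN are left to Table 3 alone

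*SAP*

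**What the plan says.** - **SAP 5.1.1, Table 3.** For PegIFN recipients, Period 1 ends at "Min [Date of first PegIFN- α 2a intake - 1 day, cut-off date ^b" (the earlier of the two). For participants without PegIFN it ends at "Date of Week 12 study agent intake - 1 day". Period 2 starts on the corresponding dosing date. No clock time enters.
- **SAP 5.1.2.2** repeats the date-only start: "The treatment period 2 start date (TP2 Day 1) is defined as the date of first PegIFN- α 2a injection". The Week 12 agent intake date is used for those without PegIFN.
- **SAP 5.1.3, Table 4.** Period 1 has its own Week 12 time point, "Week 12 period 1", with target Day 85 and window 82 to 92. Footnote a says that an assessment made before PegIFN, judged by date and time, "will be considered under treatment period 1 (Week 12 period 1"). Footnote b says: "End of treatment period 1 (EOT1) visit will be the last visit of treatment period 1". The same section allocates visits to time points within each phase.
- **Protocol 1.3, footnote d:** "All assessments (with the exception of the sparse and intensive PK samples) should be performed before administration/intake of JNJ-3989 and NA". PegIFN is preferably self-injected in the evening. Footnote m starts the 12 weekly injections at Week 12.

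**The concern.** At Week 12 the plan is to sample and then dose on one day. A date-only boundary cannot separate the two, whereas a date-and-time boundary can. The SAP contains both and does not rank them, so two programmers could produce different by-phase tables from the same data.

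The difference matters because Week 12 is the one scheduled look at the full 12 weeks before PegIFN is added. The end-of-period-1 visit (EOT1) enters analyses over time by default (SAP 5.1.3). The Period 1 nadir is meant to cover the first 12 weeks (5.4.1.2.1). Safety assessments are presented by phase (5.6), and worst-case laboratory, ECG and vital-sign results are derived within phase (5.6.3.1, 5.6.3.3, 5.6.3.4). A hematologic, hepatic or renal abnormality present before any PegIFN could therefore be tabulated in the PegIFN phase.

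**Working it through.** The plan states no figure on this point, so the check applies each rule to the scheduled visit days.

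**Inputs.** Post-baseline visits up to Week 12 are on Days 15, 29, 57 and 85 (Protocol 1.3). Phase boundaries come from SAP Table 3; windows and footnotes a and b come from Table 4.

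**Case 1: Week 12 sample and first PegIFN both on Day 85.**
- Table 3: Period 1 ends on Day 85 − 1 = Day 84, and Period 2 starts on Day 85. The pre-dose sample is in Period 2 and the Period 1 Week 12 time point is empty. No visit is scheduled between Weeks 8 and 12, so EOT1 is Week 8, Day 57.
- Footnote a: the sample precedes PegIFN, so it is in Period 1 and EOT1 is Day 85.
- Difference in EOT1: 85 − 57 = 28 days.

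**Case 2: sample on Day 85, first PegIFN on Day 86.** Table 3 ends Period 1 on Day 86 − 1 = Day 85. Both rules put the sample in Period 1, and there is no conflict.

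**Case 3: no PegIFN, Week 12 JNJ-3989 on Day 85.** Footnote a is tied to PegIFN administration and gives no rule. Table 3 ends Period 1 on Day 84, the sample takes the Period 2 Week 12 label, and EOT1 is Day 57. If footnote a is honoured for recipients, the same visit carries different labels in the two subsets.

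**What Table 3, applied literally, removes from Period 1** (post-baseline draws, from the Schedule of Activities as extracted):

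| Assessment | Scheduled weeks in Period 1 | Moved to Period 2 |
|---|---|---|
| Chemistry, hematology | 2, 4, 8, 12 | 1 of 4 |
| Quantitative HBsAg | 4, 8, 12 | 1 of 3 |
| 12-lead ECG | 4, 12 | 1 of 2 |
| Renal biomarkers | 12 | 1 of 1 |

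The HBsAg nadir for Period 1 would then rest on Weeks 4 and 8. The by-phase renal summary (SAP 5.6.3.2) would have no scheduled post-baseline retinol binding protein or beta-2-microglobulin value in Period 1.

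**The case against.** The strongest reply is that footnote a was written for exactly this sample. Table 4 creates a Period 1 Week 12 row that strict use of Table 3 would leave empty in the planned case, so Table 3 cannot be meant literally, and the more specific rule should govern. That is a fair reading of intent for PegIFN recipients. A reader might infer that the SAP simply makes Week 8 the end of Period 1. The documents do not support that as a flat statement, because it follows only if Table 3 is allowed to override the footnote. What survives is that no precedence is stated, that 5.1.2.2 repeats the date-only rule, and that allocation within phase suggests phase is set first.

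A second reply is that little depends on the boundary for efficacy. A reader might infer that the Period 1/Period 2 split is the only within-trial view of what PegIFN adds. It is not: SAP 5.1.5 defines a Reference Timepoint as the last value before the first PegIFN dose. Changes from it are planned for HBsAg, HBeAg, HBV DNA, HBV RNA and HBcrAg, and none of these depends on the phase boundary.

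A third reply concerns participants without PegIFN. They stay on the Period 1 regimen to Week 24, so their boundary marks no change of treatment and cannot attribute their own abnormalities to PegIFN. That stands. For them the defect is inconsistent labelling and a misplaced EOT1.

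**Conclusion.** The two rules conflict in the current SAP for every PegIFN recipient sampled and first injected on the same date, which is the planned case. For participants without PegIFN there is a gap and not a conflict; the documents do not say how many there will be.

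If Table 3 is applied, EOT1 moves back 28 days and the draws tabulated above move into Period 2. The consequence of most weight is in safety: pre-PegIFN Week 12 laboratory, ECG and renal biomarker values would be reported in the PegIFN phase in by-phase and worst-case summaries.

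This rests on three assumptions: sample and dose share a date, the sample precedes PegIFN, and no unscheduled visit falls between Week 8 and the boundary (such a visit would become EOT1). Footnote d fixes the order relative to JNJ-3989 and NA. That PegIFN follows the sample is inferred from the preferred evening injection.

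The Week 24 primary endpoint is untouched. A reader might take the 28-day shift as a third of Period 1 exposure lost (28 of 84 days). It is only the gap between two sampling visits. Exposure is calculated from dosing dates (SAP 5.6.1), and none is lost.

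**What to change.** 1. In Table 3, for assessments, set the Period 1/Period 2 boundary at the date and time of the first PegIFN injection or, for participants without PegIFN, of the Week 12 JNJ-3989 injection. Add a sentence to 5.1.2.2 that same-day assessments before that dose belong to Period 1.
2. Extend Table 4 footnote a to participants without PegIFN on the same basis, so that all pre-dose Week 12 assessments carry one label.
3. Where a time is missing, assign scheduled Week 12 non-PK assessments on the dosing date to Period 1, in line with the protocol's sampling order.

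The Week 12 JNJ-3989 dose already falls in Period 2 under Table 3, which agrees with the compliance denominator of 3 injections per period (SAP Appendix 7), so no change is needed there.

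The cost is SAP wording in three places and one phase-derivation step. Trial conduct, data collection and sample size do not change.
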